1.2 Primary Study Endpoints

The primary endpoint for the study is creatinine-corrected urinary NNAL concentration at 6 weeks (after switching).

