7.2.4 Switching Phase – Visit 2 (Day 21 ± 7 days)

The following procedures will be completed in a private clinic space in the Clinical Research Center. Participants and researchers will be wearing appropriate PPE at all times, except for noted measures where the participant will need to remove their mask (when COVID protocols apply).

Prior to the visit:

7.2.4.1 Participants will then be provided with instructions to complete measures via a home computer/smart phone (see table of measures). A link to the surveys in REDCap will be sent to the participant's email address or phone the day of the clinic visit. Participants will be instructed to complete all questionnaires within 24 hours. Participants unable to complete the questionnaires at home via a computer/smart phone will be called by the researchers to complete the questionnaires.

(Part A): Participant Check-In

7.2.4.2 The following measures will be completed:

- **7.2.4.2.1** Adverse events will be documented, and any concomitant medication changes will be recorded.
- **7.2.4.2.2** The cigarette and study product use diary will be collected by the researcher and entered into Daily Cigarette and E-cig Use Diary Log in Redcap.
- **7.2.4.2.3** Use of other tobacco products in the past 7 days will be assessed via the Other Tobacco Use form.
- **7.2.4.2.4** Participants will be encouraged to remain abstinent from cigarettes.
- **7.2.4.2.5** Participants will be instructed to complete daily diaries related to their study product and cigarette use (E-cigarette Daily Diary). They will also be asked to return all used and unused e-cig pods at their next study visit.
- **7.2.4.2.6** Participants will be provided with a supply of pods based on their usage.

(Part B): Completion of Biomeasures

- **7.2.4.3** The participant will then leave the clinic space to have their blood pressure and weight measured.
- **7.2.4.4** Participants will then be taken to the CRC bathroom and will be asked to provide a urine sample.
 - 7.2.4.4.1 A pregnancy test will be completed for women of childbearing potential.
 - **7.2.4.4.2** Participants will complete an exhaled carbon monoxide reading.

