7.2.6 Switching Phase – Visit 3 (Day 42 -7/+14 days)

The following procedures will be completed in a private clinic space in the Clinical Research Center. Participants and researchers will be wearing appropriate PPE at all times, except for noted measures where the participant will need to remove their mask (when COVID protocols apply).

Prior to the visit:

7.2.6.1 Participants will be provided with instructions to complete measures via a home computer/smart phone (see table of measures). A link to the surveys in REDCap will be sent to the participant's email address or phone the day of the clinic visit. Participants will be instructed to complete all questionnaires within 24 hours. Participants unable to complete the questionnaires at home via a computer/smart phone will be called by the researchers to complete the questionnaires.

(Part A): Participant Check-In

- **7.2.6.2** The following measures will be completed:
 - **7.2.6.2.1** Adverse events will be documented, and any concomitant medication changes will be recorded.

- **7.2.6.2.2** The cigarette and study product use diaries will be collected by the researcher and entered into the Daily Cigarette and E-cig Use Diary Log in Redcap. Participants will stop using the diaries at this point of the study forward.
- **7.2.6.2.3** Use of other tobacco will be assessed via the Other Tobacco Use form.
- **7.2.6.2.4** All used and unused e-cig pods will be collected by the researcher for review. Participants will then be able to retain some of the unused pods based on their usage.
- **7.2.6.2.5** Participants will be encouraged to remain abstinent from cigarettes.
- **7.2.6.2.6** Participants will also verbally be provided with information regarding how they can purchase their own e-cig devices and products, similar to the one used in the study. Participants will be instructed to purchase e-liquid from reputable companies and to not buy from unknown or illicit sources.

(Part B): Completion of Biomeasures

- **7.2.6.3** The participant will then leave the clinic space to have their blood pressure and weight measured.
- **7.2.6.4** Participants will then be taken to the CRC bathroom and will be asked to provide a urine sample.
 - **7.2.6.4.1** A pregnancy test for women of child-bearing age will be completed.
- **7.2.6.5** The participants will return to the clinic space to completed the 10 minute Holter EKG.
- 7.2.6.6 Participants will complete an exhaled carbon monoxide reading.

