8.2 Sample size determination

We plan to randomize a total of 240 participants (120 in each dose group), and it is assumed that, although all efforts will be made to ensure 100% retention in the trial, as many as 30% of participants may drop-out after randomization. Thus, the effective sample size for this study could be as low as 84 per group, as the primary study endpoint is measured and collected at the last in-person study Visit 4.

Therefore, n=84 is the expected number of participants in each group to complete Visit 4 (e.g. complete the 'Switching Phase' of the study). It is expected that the NNAL levels in the nicotine-containing e-cigs group will be similar to results obtained by Goniewicz et al¹³ assuming a pre-treatment mean =225ng/ml creatinine (SD 165) vs. post-treatment 80 ng/ml creatinine (SD=69). The pre-treatment values of the placebo e-cigs group are expected to be similar to that of the nicotine-containing e-cigs group, as this measure occurs prior to randomization. The n=84 per group sample size should enable us to detect a post-treatment NNAL difference of 35 ng/ml creatinine or larger between groups (i.e., the placebo e-cigs group's post-treatment NNAL mean value be > 115), with at least 90% statistical power under 5% type 1 error.

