8.3 Statistical methods

For the analysis, the baseline time will be Visit 1, prior to randomization to an e-cig nicotine content regimen (placebo or nicotine), which occurs at end of Visit 1.

Summary statistics will be provided for baseline smoking characteristics, along with other study demographics collected upon enrollment/screening at Visit 1. Summary statistics will also be provided for all variables at each visit. This will include all randomized subjects.

Aim 1: For each battery of measures, the mean change from week 1 to week 6 will be estimated with a corresponding 95% confidence interval. The p-value for testing zero underlying change will also be provided. This analysis will be conducted separately for the two treatment arms. To adjust for multiple comparisons, the false discovery approach will be used. Additionally, the trajectory of each measurement at visit 1 visit 2 and visit 3 will be modeled using linear mixed effects regression.

Aim 2: The difference between the two treatment arms on markers of health risk will be analyzed. The primary conceptual framework is a modified intent-to-treat: subjects will be analyzed by their randomized arm regardless of compliance with the e-cig nicotine content regimen, as long as data for the particular outcome is available at either of the post-randomization visits (Visit 2 or Visit 3). The basic statistical tool will be linear regression or logistic regression. Two sets of regressions will be conducted. The first set of regressions will model the dependence of the outcome measures at week 6 on the two treatment arms while controlling for the baseline value of the outcome variable. The second set of regressions will adjust for additional covariates at baseline (V1), to be selected via backward elimination at 0.05 significance level. These additional covariates will be chosen from the following list based on appropriateness for the specific outcome variable.

- Age
- Race
- Hispanic
- Education status
- Gender
- Income
- SDOH questionnaire (ACES score)
- Baseline cpd
- Baseline CO
- Baseline NNAL
- Baseline cotinine
- Menthol/non-menthol cigarettes
- Cigarette length
- Height
- Weight
- BMI

- Baseline FEV1
- Baseline PSCDI
- Quit attempt history
- "Currently, do you have any symptoms or a disease that you believe is caused or made worse by your tobacco use?" (yes/no)
- Perceived cessation support questions
- ETS questionnaire
- Baseline MNWS
- Baseline QSU
- Baseline audit c

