We will strive to minimize the number of missing values by rigorous follow-up with the study subjects. In spite of this, we still anticipate some missing values in the final datasets. Our basic tool to address this problem is multiple imputations. More specifically, if a variable is missing at V1, it will be imputed from the distribution of that variable of non-missing subjects. Due to the randomization at V1, non-missing subjects from both arms will be used for the distribution. For values missing at V3 (6 weeks after randomization), but non-missing at V2, the value collected at V2 will be carried forward in time via the LOCF (Last Observation Carried Forward) approach. For any instance where the participant remained in the trial, but did not provide data values at either post-randomization visit (V2 or V3), that case will be excluded from the analysis (modified ITT).

For some scenario, the missing values can be imputed by some reasonable assumptions. If a participant dropped out of the study prior to Visit 3 without providing Visit 2 data for the outcome, a 'worst-case-scenario' assumption will be made – assuming that the participant reverted back to exclusive smoking of cigarettes upon dropping out of the trial. Under this assumption, their Visit 2 baseline value will be carried forward to Visit 3. See the table below for a detailed outline of these methods:

V1	V2	V3	V` Baseline Result	V3 Endpoint Result	Mechanism of Missing		
+	+	+	Use directly Use directly		N/A		
+ + -			Lise directly	Impute V3 via LOCE from V2	Dropped out between V2 and V3		
	•	-			Missing V3 due to item non-response		
+	-	+	Use directly	Use directly	N/A		
-	+	+	Impute the V2 value from the overall sample distribution	Use directly	N/A		
			Use directly	Impute V3 via LOCF from V1	Dropped out between V1 and V2 Assume 'Worst-Case- Scenario'		
+	-	-	Excluded from Analysis (N	Dropped out between V2 and V3 Item Non-Response at V2			
			Excluded from Analysis (N	Completed the Switching Phase Missing V2 and V3 due to item non-response			
	Impute the V1 value		Impute the V1 value	Impute V2 via LOCE from V2	Dropped out between V2 and V3		
-	T	-	distribution		Missing V3 due to item non-response		
-	-	+	Impute the V1 value from the overall sample distribution	Use directly	N/A		
-	-	-	Excluded from Analysis (Modified ITT)				

Stratified Imputation Approach:

(+) = non-missing data(-) = missing data

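### Filling a missing week-6 NNAL with the single week-3 value can bias the primary arm comparison, and it rests on a different dropout assumption from the plan's other rules

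*Combined protocol and SAP*

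**What the plan says.** Section 1.2 makes the primary endpoint "creatinine-corrected urinary NNAL concentration at 6 weeks (after switching", which is measured at Visit 3 (V3). Under its heading on missing values, section 8.3 of the combined protocol and SAP states: "Our basic tool to address this problem is multiple imputations". The rules for a missing V3 are nevertheless single fills or exclusion:

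- **Visit 2 (V2) present, V3 missing.** "the value collected at V2 will be carried forward in time via the LOCF (Last Observation Carried Forward) approach". The table applies this to people who leave between V2 and V3 and to item non-response.
- **Dropout with no V2 value.** The text carries the baseline value forward, "assuming that the participant reverted back to exclusive smoking of cigarettes upon dropping out of the trial".
- **Still in the trial, neither V2 nor V3 available.** Excluded under the modified intent-to-treat rule.

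For Aim 3, the same section counts all Switching Phase dropouts as non-abstainers, whether or not they attended V2. For Aim 1, trajectories over the three visits "will be modeled using linear mixed effects regression", but no arm contrast at week 6 is specified. No sensitivity analysis for missing NNAL is described.

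**The concern.** The primary comparison is meant to be at week 6. With this rule it becomes a blend of week-6 and week-3 values, weighted by how many people are lost after V2 in each arm. If NNAL is still moving after week 3, or the arms separate or converge, the blend estimates something other than the week-6 difference. A single fill also treats the filled values as if they had been observed.

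The dropout assumptions do not line up either. The stated reason for the reversion rule is that leaving the trial means returning to smoking. That reason does not depend on having attended V2. Yet a person who leaves after V2 is a smoker for Aim 3 and stays at the week-3 NNAL for the primary endpoint. Section 8.2 allows for up to 30% dropout, so this choice could affect a sizeable share of the primary data.

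**Working it through.** **1. The plan's own figure.** Section 8.2 gives 120 per arm, 30% dropout, post-treatment means of 80 (nicotine) and 115 (placebo), and SD 69. Completers: 120 × 0.70 = 84 per arm. Standard error = 69 × √(2/84) = 10.65. Then 35/10.65 = 3.29, and 3.29 − 1.96 = 1.33, which gives power of about 90.8% (90.5% with the t distribution). This agrees with "with at least 90% statistical power under 5% type 1 error". The sample size is not at fault.

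**2. Age of the carried value.** The windows are "Visit 2 (Day 21 ± 7 days", that is Days 14 to 28, and "Visit 3 (Day 42 -7/+14 days", that is Days 35 to 56. The carried value is therefore between 35 − 28 = 7 and 56 − 14 = 42 days older than the one it replaces.

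**3. Expected bias.** Let dP and dN be the shares of the placebo and nicotine arms with V2 but no V3. If those lost resemble the rest of their arm, the bias in placebo minus nicotine is

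dP × (placebo V2 mean − placebo V3 mean) − dN × (nicotine V2 mean − nicotine V3 mean).

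The documents give none of these shares or V2 means, so every input here is assumed:

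| Case (no true week-6 difference) | Arithmetic | Bias, ng/ml |
|---|---|---|
| Strong (a): week-3 gap 35, 15% lost per arm | 0.15 × 35 | 5.25 |
| Mild (a): week-3 gap 10, 15% lost per arm | 0.15 × 10 | 1.5 |
| Strong (b): both arms fall from 130 to 100; 25% placebo, 5% nicotine lost | (0.25 − 0.05) × 30 | 6.0 |
| Mild (b): same fall; 15% and 10% lost | (0.15 − 0.10) × 30 | 1.5 |

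**4. Type I error.** This was simulated as a baseline-adjusted regression on lognormal NNAL, with 120 per arm, baseline 225 (SD 165) and later coefficient of variation 69/80 = 0.86. The correlations, 0.5 with baseline and 0.7 between V2 and V3, are assumed. Across runs of 600 to 4,000 replicates:

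- Strong cases: false differences of about 5 to 7 ng/ml, type I error about 7% to 10%.
- Mild cases: about 1 to 2 ng/ml, type I error 4.8% to 5.3%.
- No arm or time effect: type I error 4.8%.
- Within-arm multiple imputation from V1 (baseline) and V2, strong cases: difference near zero, type I error at most 5.5%.

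**5. Reversion set against carry-forward.** Take V2 means equal to V3 means (80 and 115), and set late dropouts to 225 under reversion. Carry-forward then gives 35 at any dropout. Carry-forward minus reversion = (225 − 80) × dN − (225 − 115) × dP = 145dN − 110dP.

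- Equal loss: 35 × 0.15 = 5.25; 35 × 0.30 = 10.5.
- Nicotine 10%, placebo 20%: 14.5 − 22 = −7.5, so 35 against 42.5.
- Nicotine 20%, placebo 40%: 29 − 44 = −15.
- Nicotine 40%, placebo 20%: 58 − 22 = +36.

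If V2 shows only 75% of the fall from baseline, the shift for equal loss of 10% to 30% is +2.6 to +7.9. These figures are gaps between two assumptions, not a bias against a known truth.

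**6. Whether imputation cures reversion.** It does not. When late dropouts were simulated as reverting, multiple imputation gave 34.6 to 36.0 where the truth was 29.1 to 31.4 (15% lost per arm). It gave 35.0 to 35.5 where the truth was 41.3 to 42.8 (10% nicotine, 20% placebo). Carry-forward errs in the same way.

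**The case against.** The best defence is that the rule is explicit and ordered: use the last observed value, V2 if there is one and baseline otherwise. A reader might infer that section 8.3 contradicts itself. It does not. The reversion rule is confined to dropouts without V2 data, so no case falls under two rules. What remains is an inconsistency of assumption, clearest against Aim 3.

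A reader might also infer that late dropouts are all set to a successfully switched level. They carry their own measured V2 value. The plan analyses people regardless of compliance and expects only 40% (nicotine) and 20% (placebo) of completers to be abstainers. Someone still smoking at V2 carries a smoking-level NNAL.

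The strong cases are demanding. One needs a full 35-unit gap at week 3 that has gone by week 6; the other needs five-fold differential loss. The 30% is an upper figure for all dropout, not for loss after V2. The mild cases are nearly harmless. The Aim 1 mixed model is also a partial check, though not on the arm contrast.

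These objections limit the size of the problem. They do not supply a reason to prefer a single week-3 fill for a week-6 primary endpoint.

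**Conclusion.** The point holds in conditional form. The carry-forward rule can bias the week-6 comparison and distort its type I error when the arm gap changes after week 3, or when NNAL is moving and late loss differs by arm. Under assumed inputs the effect runs from negligible to about 5 to 7 ng/ml, that is 14% to 20% of the 35-unit target (5/35 and 7/35). The direction cannot be fixed in advance. The documents do not support saying that the result will be shifted, because they give no V2 NNAL, no correlations, and no dropout by arm or visit.

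The mismatch with the other dropout rules is real, but it is one of assumption. It concerns dropouts only: reversion has no bearing on item non-response among people still in the trial. It would also be wrong to infer that a mixed model or multiple imputation settles the reversion question. Both assume missing at random, so reversion needs an analysis of its own.

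**What to change.** In section 8.3 and its table, for Aim 2:

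1. Replace the entries that fill V3 from V2. Use either a mixed model on V1, V2 and V3 (visit categorical, arm-by-visit term, arm contrast at week 6) or true multiple imputation within arm from V1 and V2, with variances combined across imputations. Keep the carry-forward as a sensitivity analysis.
2. State what happens under the chosen method to the row that carries baseline forward for dropouts before V2. That row already sits awkwardly with the modified intent-to-treat definition, which requires outcome data at V2 or V3.
3. Add a sensitivity analysis that carries baseline forward for all dropouts, before and after V2, but not for item non-response among people still in the trial.

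The cost is SAP wording and some programming, with no new data. The drawback is that the primary result then rests on a missing-at-random assumption, which is why item 3 belongs with item 1.

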- Baseline cigarette perceived health rick score
- E-cig Perceived risk/Perceptions of e-cig risks (from screener)
- Baseline CESD
- Baseline Kessler 6
- Baseline perceived stress
- Baseline COPD questionnaire
- Baseline interheart
- Importance and confidence to quit

Same strategy will be used for withdrawal items on the MNWS and scores on ratings of cigarette craving. The analysis will be conducted for the values of these variables at week 3, however.

Cigarette Abstainers Subgroup Analysis

In addition to the intent-to-treat analysis, additional analysis on subgroup of regular cigarette abstainers only will be conducted. By design, this subgroup will only consist of Switching Phase Completers (still in the study at the time of V3) who have successfully abstained from cigarette and other tobacco use (except e-cigs) from 1 week prior to V2 consistently and consecutively until V3. Therefore, this subgroup would be defined as 'quit' for at least 4 weeks. Participants in this sub-group must also have an exhaled CO < 6 ppm at both V2 and V3. Based on our previous data, we believe that 40% of the nicotine e-cig group (84 x .40 = roughly 33 participants) and 20% of the placebo e-cig group (84 x .20 = roughly 16 participants) will be classified as abstainers. For this relatively small subgroup, we shall only model the dependence of the outcome measures at week 6 on the two treatment arms while controlling for the baseline value of the outcome variable. No elaborate adjustment of other covariates will be included.

Aim 3: The proportions of subjects who will try to abstain from cigarettes and who will continue to use an e-cig at week 10 will be compared between the two arms using Fisher's exact test. Switching Phase dropouts will be treated as 'non-abstainers' from cigarettes under the 'worst case-scenario' assumption. A supplementary logistic regression will also be conducted to explore their dependence on demographic variables in addition to the two treatment arms.

Multiple imputation for missing values

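### Section 8.3 gives conflicting rules for dropouts with no post-randomization NNAL value, and the power in Section 8.2 makes no allowance for carrying baseline forward

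*Combined protocol and SAP*

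**What the plan says.** The primary endpoint is creatinine-corrected urinary NNAL at 6 weeks (Section 1.2). These parts of the plan decide who is analysed and with what value.

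- **Section 8.3, Aim 2.** The primary framework is a modified intent-to-treat analysis. Participants are analysed in their randomized arm "as long as data for the particular outcome is available at either of the post-randomization visits (Visit 2 or Visit 3"). There is no exception for dropouts. The first model regresses the week 6 value on arm and baseline.
- **Section 8.3, missing-data text.** Exclusion is confined to a narrower case: "For any instance where the participant remained in the trial, but did not provide data values at either post-randomization visit". If instead a participant "dropped out of the study prior to Visit 3 without providing Visit 2 data for the outcome, a 'worst-case-scenario' assumption will be made", and "their Visit 2 baseline value will be carried forward to Visit 3".
- **Section 8.3, imputation table.** Among participants with a Visit 1 value only, those who left between Visits 1 and 2 are kept ("Impute V3 via LOCF from V1"). The entry "Dropped out between V2 and V3 Item Non-Response at V2" is excluded, as are those who completed the switching phase with both values missing.
- **Section 8.3, Aim 3.** "Switching Phase dropouts will be treated as 'non-abstainers' from cigarettes", again as a worst case.
- **Section 8.2.** With 120 randomized per arm and up to 30% dropout, power is calculated on 84 per arm: at least 90% for a difference of 35, with 5% type 1 error. Imputed values are not mentioned.

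**The concern.** A participant who leaves with no NNAL value after randomization is out of the primary analysis under the Aim 2 paragraph and in it, at the smoking baseline, under the missing-data text. Nothing in the plan says which rule governs, so the choice could be made after the data have been seen.

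The rules also give different results. Exclusion compares people with observed values. Carry-forward adds people at a mean near 225 to arms expected at 80 and 115. This shrinks the difference, widens the spread and makes the estimate depend on which arm loses more people. Section 8.2 allows for dropout only by reducing the sample size, which fits exclusion but does not describe carry-forward.

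**Working it through.** **1. The three statements side by side.** For a participant with a Visit 1 (V1) NNAL value and none at Visit 2 (V2) or Visit 3 (V3):

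| Participant | Aim 2 paragraph | Missing-data text | Imputation table |
|---|---|---|---|
| Left between V1 and V2 | Excluded | Kept, baseline carried | Kept, V1 carried |
| Left between V2 and V3, NNAL missing at V2 | Excluded | Kept, baseline carried | Excluded |
| Stayed in, NNAL missing at both | Excluded | Excluded | Excluded |

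Only the last row agrees throughout. The second group is probably small.

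**2. The plan's own power.** Inputs from Section 8.2: n = 84 per arm, difference 35, SD 69. A two-sided 5% test and the same SD on placebo are assumed. The noncentrality is 35/69 × √(84/2) = 3.29. The normal approximation gives Φ(3.29 − 1.96) = 90.8%, and the t-test gives 90.5%. The stated figure reproduces.

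**3. Expected estimate.** Let f_N and f_P be the nicotine and placebo shares with no later value. Section 8.2 gives means of 225 (baseline), 80 (nicotine) and 115 (the placebo threshold). The carry-forward estimate is [(1 − f_P) × 115 + f_P × 225] − [(1 − f_N) × 80 + f_N × 225].

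| f_N / f_P | Carry-forward | Exclusion |
|---|---|---|
| 15% / 15% | 0.85 × 35 = 29.75 | 35 |
| 30% / 30% | 0.70 × 35 = 24.5 | 35 |
| 25% / 35% | 153.5 − 116.25 = 37.25 | 35 |
| 35% / 25% | 142.5 − 130.75 = 11.75 | 35 |

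The plan does not split dropout by timing or arm, so these are scenarios. Of 240 participants, 72 are affected if all 30% leave before V2, 36 if half of them do, and 12 if the share is 5%.

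**4. Power under carry-forward.** Without baseline adjustment, at a 30% share, the mixture SDs are 126.2 (nicotine) and 118.5 (placebo). The standard error is √((126.2² + 118.5²)/120) = 15.8, and power is Φ(24.5/15.8 − 1.96) = 34%.

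The planned model adjusts for baseline, so it was simulated: 120 per arm, lognormal NNAL, baseline 225 (SD 165), later values 80 or 115 (SD 69), dropout equal and at random, 20,000 runs per cell. The plan gives no baseline correlation; 0.3, 0.5 and 0.7 on the log scale are assumed.

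| Share with no later value | Estimate | Power at 0.3 / 0.5 / 0.7 |
|---|---|---|
| 5% | about 33 | 90 / 94 / 97% |
| 8% | about 32 | 85 / 89 / 94% |
| 10% | 31.5 | 80 / 85 / 91% |
| 15% | about 30 | 71 / 75 / 83% |
| 30% | 24.5 | 45 / 49 / 56% |

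Power of 90% is kept up to a share of about 5%, 7% and 11% respectively, or about 4% without baseline adjustment. Exclusion at 30% gives 91 / 94 / 98%.

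**5. No true effect.** With both arms at 80 and shares of 25% / 35%, carry-forward is expected to show (0.35 − 0.25) × (225 − 80) = 14.5. It rejects in 18% to 22% of trials, or 12% to 13% if dropout counts are fixed instead of random. This requires that all dropout precedes V2 and that no dropout returned to baseline smoking. With equal 30% shares, rejection is 4.6% to 4.9%, so there is no inflation.

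**6. Error of each rule.** At 30% / 30%, if every dropout reverted, the difference over all randomized participants is 24.5, and exclusion overstates it by 10.5. If none reverted, it is 35, and carry-forward understates it by 10.5. Under full reversion, exclusion understates by 2.25 at 25% / 35% and overstates by 23.25 at 35% / 25%.

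**The case against.** - **The specific rule may govern.** The Aim 2 paragraph can be read as a framework, with the missing-data text and table as its operating rules. Aim 3 uses the same worst-case idea, so carry-forward may well be intended. This does not settle the matter: the Aim 2 paragraph makes availability of data a condition of entry, Section 8.2 counts dropouts out, and the text and table disagree with each other.
- **Section 8.2 contains no arithmetic error.** This stands. The 30% is a stated upper limit, and dropouts with a Visit 2 value stay in under either rule, so more than 84 per arm would normally be analysed. The power point applies only if carry-forward governs and the share without later values passes about 5% to 11%.
- **The largest figures are extreme cases.** They are. The 45% to 56% power needs the full 30% to leave before Visit 2, and the inflated rejection needs several conditions together.
- **Lower power is partly a different target.** Also fair: if dropouts return to smoking as before, the smaller carry-forward difference is the correct one for all randomized participants. That is a reason to choose the rule openly; it does not justify leaving two in the plan.

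**Conclusion.** The concern holds and must be fixed. The primary NNAL analysis set is not uniquely defined, whatever the dropout rate turns out to be. Equal 30% dropout without later values would separate the two rules by 35 − 24.5 = 10.5, against a design difference of 35.

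The power finding is conditional. The stated 90% agrees with exclusion; under carry-forward it depends on a pre-Visit 2 dropout share that the plan does not give. The contradiction rests on the text alone. The sizes rest on the Section 8.2 means and SDs, an assumed placebo SD of 69, lognormal values, the assumed correlations, and remaining participants (including dropouts with a Visit 2 value) following the stated post-treatment distribution. Neither rule is free of bias.

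**What to change.** State one rule for the primary NNAL analysis, worded identically in the Aim 2 paragraph, the missing-data text and the table. Say whether it also covers the other outcomes, since the missing-data text and table apply to all of them. The choice is the sponsor's.

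- **Option A, exclusion primary.** Keep the Aim 2 paragraph and the Section 8.2 power. Change the worst-case sentence and the table entry for dropout between Visits 1 and 2 to exclusion. Name baseline carried forward as a sensitivity analysis.
- **Option B, baseline carried forward primary.** Add to the Aim 2 paragraph that participants who drop out before Visit 3 with no Visit 2 value are included, with the Visit 1 value carried to Visit 3. Change the table entry for dropout between Visits 2 and 3 to match. Restate the power for a range of pre-Visit 2 dropout, for example 5%, 15% and 30%, and report the exclusion analysis alongside.

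Under either option, report dropout without later values by arm. A tipping-point multiple-imputation analysis, from no reversion to full reversion to the Visit 1 value, would be a useful optional addition.

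Editorial: the baseline label in "their Visit 2 baseline value will be carried forward to Visit 3" and the baseline-column entry "Impute the V2 value from the overall sample distribution" should both refer to Visit 1, as Section 8.3 defines baseline.

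The cost is wording, one or two table rows and one added analysis, with no new data. Option B may lower the stated power.
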